Study Protocol

Title of Project: A Chatbot Intervention for Reducing HPV Vaccine Hesitancy
NCT #: NCT05959564
November 16, 2022

INITIAL APPLICATION PART 2

1. Abstract:

The goal of this project is to test the efficacy of a chatbot intervention for reducing HPV vaccine hesitancy among African American parents. This project has two phases. In phase I, in-depth interviews will be conducted with African American parents to evaluate the feasibility and acceptability of the chatbot intervention. In phase II, an online experiment will be conducted to test the effectiveness of the chatbot intervention with African American parents. Results of this project will inform future communication interventions for reducing vaccine hesitancy among African American parents.

2. Subject Selection:

- a. **Recruitment:** In phase I, we will recruit participants from local pediatric offices. We will recruit by distributing flyers in the offices. We will obtain permission from the practices to recruit at their offices. A copy of the flyer is attached to this application (we will submit an addendum if additional changes need to be made to the flyer before distribution). In phase II, participants will be recruited from online survey panels (e.g., Prolific, YouGov, Lucid, etc.). Eligible participants will be invited via email to participate in the study. There will also be screening questions at the beginning of the survey to screen participants to ensure they meet the eligible criteria.
- b. **Eligibility Criteria:** Participants must be 18 years or older, self-identify as African American, are custodial parents or caretakers of a child under the age of 18.
- c. **Rationale:** The burden of HPV-associated diseases (e.g., cervical cancer) is disproportionately higher among African Americans compared to other racial groups. Understanding effective methods of communicating to African American parents about the importance of HPV vaccination is therefore critical.
- d. **Enrollment Numbers:** For phase I, we aim to recruit up to 30 participants. For phase II, we aim to recruit up to 600 participants.
- e. **Rationale for Enrollment Numbers:** The enrollment numbers ensure we have adequate statistical power to detect small effects of the intervention.

3. Procedures:

For phase I, we will conduct in-depth interviews with up to 30 African American parents recruited from local pediatric offices. To facilitate participation, the interviews will be conducted online via Zoom. During the interviews, participants will be asked to interact with a chatbot designed to answer questions about HPV vaccines. Their opinions about the chatbot and suggestions for improvement will be solicited. Each interview session will last approximately 45 minutes. Only anonymized transcription (using Zoom's transcript function) of the interview will

be saved for later analysis. Interviews will not be audio- or video-taped. Each participant will receive a \$50 store gift card. The cash incentive is needed to encourage participation in the study.

In phase II, participants will complete an online survey. In the survey, participants will first answer questions related to their attitudes toward childhood vaccines. Then they will be directed to interact with a chatbot designed to deliver personalized HPV vaccine messages (tailed to the participant's personality) or a similar chatbot with non-personalized messages. There will also be a control condition where participants receive no HPV vaccine messages. After interacting with the chatbot, participants will answer questions related to their attitudes toward HPV vaccination, intentions to vaccinate their children, as well as other message response measures. Those in the control will answer the same questions without interacting with a chatbot. The survey will take approximately 10 minutes to complete. Participants who complete the survey will be compensated with a small amount of cash paid through the online survey platform (\$1-\$2).

4. Risks:

There are no known risks associated with this research. Participants may opt to exit the interview or survey if they are not comfortable answering any of the questions.

5. Benefits:

There are no direct benefits to participants. This research will result in an improved understanding of the design of effective educational materials about HPV vaccination.

6. Confidentiality:

Responses of the participants will be confidential. The transcriptions from the interviews will have no identifying information. The transcriptions will not be linked in any way to personally identifiable information. The questionnaires will not contain any questions that ask for information that could be used to identify the participants. Only approved researchers will have access to the data collected. Hard copy materials will be stored in a locked office. Data collected will be stored in a password-protected computer located in a room with limited access. All research data collected from this study will be stored for 10 years after the study allow the research team to thoroughly analyze the data for research purposes only. The research data will be removed from computer hard disks afterwards.

7. Consent Process:

Because this study involves online interviews and an online survey, we request a consent waiver because our research meets the following criteria: (1) this research involves no more than minimal risk to the subjects (no personally identifiable information is collected); (2) the waiver or alteration will not adversely affect the rights and welfare of the subjects (participants can stop their participation at any time during the study). The online consent form (see attached) is identical to a written consent form; (3) the research

could not practicably be carried out without the waiver or alteration (written signatures cannot be collected online). Participants will indicate consent by clicking a radio button. Online consent will be obtained prior to the study. Participants will be permitted to print/save a copy of the consent form for their records; and (4) the subjects will be provided with additional pertinent information after participation through the debriefing process (see attached).

Participants who agree to participate will indicate consent by clicking a radio button in an online questionnaire ("I agree to participate") before the start of the study (for both the online interview and the onine survey). No name will be required. Because the interviews are one-on-one, investigators will know whether or not a participant agrees to participate by examining the instantly recorded responses in the online questionnaire. There is no deception involved in either study.

The title of the IRB application (Chatbot and Vaccine Acceptance) is different from the title on the consent forms (HPV Vaccine Messaging Study). We want to keep the title on the consent forms general because some of the participants will not interact with a chatbot.

8. Conflict of Interest:

There is no conflict of interest.

9. HIPAA Compliance:

N/A

10. Research Outside of the United States:

N/A

11. Research Involving Prisoners:

N/A

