Statistical Analysis Plan

Title of Project: A Chatbot Intervention for Reducing HPV Vaccine Hesitancy

NCT #: NCT05959564

January 14, 2023

We will conduct Analyses of Covariance (ANCOVAs) and multiple regressions to examine the group differences. The primary dependent variables will consist of parents' attitudes and intentions toward vaccinating their children against HPV (both are continuous variables). Secondary dependent variables will consist of chatbot ratings. In ANCOVAs, the key independent variable will be chatbot (personalized, non-personalized, no chatbot control). Covariates will include key demographic variables such as age, gender, and education. In regression analyses, a block structure will be used where the first block will consist of the control variables (i.e., covariates) and the second block will contain the key predictor variables—dummy-coded chatbot variables. We will report standard descriptive statistics and correlation matrices for all key variables.

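### The SAP does not use the vaccine-attitude score taken before exposure, so if the effect varies with baseline attitude the trial cannot say whether less favourable parents moved

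*Protocol*

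**What the plan says.** Protocol section 1 (Abstract) sets the aim: to "test the efficacy of a chatbot intervention for reducing HPV vaccine hesitancy among African American parents". Under section 2b, participants must be adults who "self-identify as African American, are custodial parents or caretakers of a child under the age of 18". The screening questions described in section 2a serve to "screen participants to ensure they meet the eligible criteria", so they add no test of hesitancy. Section 3 states that in the phase II survey "participants will first answer questions related to their attitudes toward childhood vaccines", before any chatbot contact. HPV attitudes and intentions follow afterwards.

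The SAP makes HPV attitudes and intentions the primary outcomes, both continuous. On the model it says: "In ANCOVAs, the key independent variable will be chatbot (personalized, non-personalized, no chatbot control". Age, gender and education are given as examples of demographic covariates. The regression enters covariates first and dummy-coded arm variables second. The SAP does not mention the pre-exposure attitude items, an interaction of arm with baseline, or a hesitant subgroup. On size, section 2d says "For phase II, we aim to recruit up to 600 participants", and section 2e claims "adequate statistical power to detect small effects of the intervention".

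**The concern.** The title and aim speak of hesitancy, but the analysis yields average arm differences over parents who range from firmly favourable to firmly reluctant. An average is a mixture. If the chatbot works mainly on reluctant parents, it is diluted by those with little room to move. If it works mainly on parents already well disposed, a positive average says little about reluctant ones. The survey collects a measure that could help tell these cases apart, and the SAP leaves it unused. At stake is how the result may be worded: whether a positive average can be described as hesitant parents having moved, and whether a null average means that they did not.

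**Working it through.** **The plan's own figure.** Section 2 gives up to 600 participants with no effect size, alpha, power, SD or allocation ratio, so 600 cannot be reproduced. Assume random allocation in equal numbers (600/3 = 200 per arm), SD 1 and two-sided alpha 0.05. Pairwise power for d = 0.20 is then 51%, and the smallest effect detectable with 80% power is 2.80 × √(2/200) = 0.28 SD.

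**Further assumptions.** The documents give neither the hesitant share h nor any subgroup effect. I take h = 25% to 50%, and d = 0.40 in one group with 0 in the other. These are deliberately extreme. Power for the two-sample contrasts is from the noncentral t.

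**Whole-sample effect.** d_all = h × d_hesitant + (1 − h) × d_other.

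| | h = 25% | h = 50% |
|---|---|---|
| Effect only in hesitant parents: d_all | 0.25 × 0.40 = 0.10 | 0.50 × 0.40 = 0.20 |
| Whole-sample power, 200 per arm | 17% | 51% |
| Power within hesitant parents | 51% (50 per arm) | 80% (100 per arm) |
| Effect only in the others: d_all | 0.75 × 0.40 = 0.30 | 0.50 × 0.40 = 0.20 |
| Whole-sample power, 200 per arm | 85% | 51% |

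At h = 50% the two opposite situations give the same average, 0.20, so the average cannot distinguish them. If the effect is uniform, d_all equals the effect in hesitant parents and nothing is lost.

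**What a split of the sample could show.** With the score dichotomised, the interaction has SE = √[2/(200h) + 2/(200(1 − h))].
- h = 25%: √(2/50 + 2/150) = 0.231. Power for 0.40 versus 0 is Φ(0.40/0.231 − 1.96) = 41%. Minimum detectable difference at 80% power: 2.80 × 0.231 = 0.65 SD.
- h = 50%: √(2/100 + 2/100) = 0.200. Power is Φ(2.00 − 1.96) = 52%. Minimum detectable difference: 2.80 × 0.200 = 0.56 SD.

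The 95% half-width within hesitant parents is 1.96 × √(2/n): 0.39 SD at n = 50 and 0.28 SD at n = 100 per arm.

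**With the score kept continuous.** Under a linear interaction and residual SD 1, the arm contrast at a baseline value 1 SD below the mean has SE √[(2/200)(1 + 1)] = 0.141. Its half-width is 0.28 SD, against 1.96 × √(2/200) = 0.20 for the all-parent contrast. The 1 SD value is only an example.

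**Gain for the main contrast.** If covariates explained 25% of outcome variance (assumed), the residual SD would be √0.75. Power at d = 0.20 would rise from about 52% to 64% by the normal approximation.

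**The case against.** The strongest reply is that the aim concerns African American parents, not hesitant ones. Hesitancy can be read as a continuum, the outcomes are continuous, and lowering its average in the named population is a coherent question that the all-parent contrast answers. That stands. A reader might infer that neither a positive nor a null average would address the stated aim; the documents do not support this.

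A reader might also infer that the trial is exposed to error in both directions at once. The dilution case supposes that favourable parents are near the ceiling and cannot move. The reverse case has those same parents improving by 0.40. Each is possible, but they rest on opposing premises and cannot be added together.

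It is fair to say, too, that the subgroup effects are assumed extremes. Making a hesitant stratum the sole support for any hesitancy claim would be a poor bargain if the effect is uniform: at d = 0.20 the stratum (50 to 100 per arm) has 17% to 29% power, against 51% overall. The baseline items cover childhood vaccines in general. A parent may accept routine vaccines and still hesitate over HPV, and the documents do not show how the items are scored. Finally, the covariate list is illustrative, so baseline attitude might yet be included. Adjustment alone would improve precision, but it would not show how the effect varies with baseline.

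These points rule out replacing the primary contrast. They do not answer the remaining gap: no prespecified analysis uses the pre-exposure score.

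**Conclusion.** The point holds in a limited form. The all-parent contrast is a valid average effect on attitudes and intentions, and it is also right for hesitant parents if the effect is uniform. The plan neither states nor examines uniformity. If the effect varies, the average cannot show whether less favourable parents moved: d = 0.40 confined to a hesitant 25% to 50% appears as 0.10 to 0.20, with 17% to 51% power. This rests on 200 per arm, SD 1, two-sided 0.05, the assumed hesitant share and zero effect in the others. The range is an illustration, not a forecast. The documents do not support the stronger inference that the trial is bound to mislead about hesitancy, or that it had to enrol only hesitant parents. What remains is an inexpensive improvement to the SAP and a limit on the wording of conclusions.

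**What to change.** In the SAP:

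1. Keep the all-parent arm contrasts as primary.
2. Add the pre-exposure attitude score as a continuous covariate in the ANCOVA and in the first regression block.
3. Prespecify, as secondary, an interaction of arm with the centred baseline score. Report arm contrasts with confidence intervals at a low baseline value fixed before results are seen.
4. Describe the all-parent result as an effect on mean attitudes and intentions in unselected parents. State that hesitant parents moved only if the low-baseline contrast supports it.

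The cost is some SAP wording and the added model terms, with no new data. The interaction is underpowered, so the low-baseline estimate and its interval should be read rather than the interaction p-value, and that interval will be wide. The extra comparisons must be labelled secondary, since there are already two primary outcomes and three arms. The report should say that the baseline items are a proxy for HPV hesitancy.

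### Only the chatbot arms meet an HPV-message task before the primary outcomes, so differential dropout could favour them; the SAP should adjust for the vaccine attitude already collected first

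*Protocol*

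**What the plan says.** The phase II flow is in Protocol section 3 (Procedures). In every arm, "participants will first answer questions related to their attitudes toward childhood vaccines". The paths then part. In the two chatbot arms the outcomes follow the task: "After interacting with the chatbot, participants will answer questions related to their attitudes toward HPV vaccination". In the third arm, "Those in the control will answer the same questions without interacting with a chatbot". On payment: "Participants who complete the survey will be compensated". Sections 4 (Risks) and 7 (Consent Process) leave participants free to stop.

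The SAP plans ANCOVAs and block regressions in which "the key independent variable will be chatbot (personalized, non-personalized, no chatbot control"). On adjustment it says: "Covariates will include key demographic variables such as age, gender, and education". The childhood-vaccine attitude is not named. The SAP defines no analysis population, gives no rule for people who leave before the outcomes, and plans no comparison of loss by arm.

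**The concern.** Two of the three arms contain an extra point at which a parent can leave after assignment and before the primary outcomes, and that point consists of HPV vaccine messages. In a study of vaccine hesitancy, reluctance is a plausible reason to leave there, and it is closely tied to the outcome. If that happens, the chatbot parents who still have outcomes are, on average, more favourable to vaccination than the controls, whatever the chatbot did. Adjusting for age, gender and education does little about this unless those variables predict attitude. The variable that would help most is measured before the chatbot but is not in the stated model.

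The stake is the size of a spurious difference relative to the effect sought. The protocol aims at small effects: "The enrollment numbers ensure we have adequate statistical power to detect small effects of the intervention".

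**Working it through.** **Plan's own figures.** There is no dropout or bias figure to reproduce. The sample size ("For phase II, we aim to recruit up to 600 participants") cannot be reproduced either, because no alpha, power, effect size or SD is given. It serves here only to set 600 / 3 = 200 per arm; equal allocation is an assumption.

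**Assumed inputs (none is in the documents).** No true effect. Baseline attitude B and outcome Y each have SD 1 and correlation r = 0.5 to 0.6. Loss is 5% in control and 10% to 25% in a chatbot arm. The odds of staying rise by a factor OR = 1.5 to 3 per SD of more favourable attitude, in all arms. Demographics carry no information on attitude.

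**Case 1: dropout follows baseline attitude.** The chance of staying is p(B) = 1 / (1 + exp(-(a + ln(OR) x B))), with a set to give the stated loss. The mean baseline among those retained is m = E[B p(B)] / E[p(B)], by numerical integration. Bias = r x (m chatbot - m control). Type I error for one chatbot arm versus control, one outcome, two-sided 5%, is Phi(bias/SE - 1.96) + Phi(-bias/SE - 1.96), with SE 0.104 to 0.109 from the numbers retained.

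| Loss, control / chatbot | OR | r | m control | m chatbot | Gap | Bias (SD) | Type I error |
|---|---|---|---|---|---|---|---|
| 5% / 10% | 1.5 | 0.5 | 0.020 | 0.040 | 0.020 | 0.010 | 5.1% |
| 5% / 15% | 2 | 0.5 | 0.034 | 0.098 | 0.064 | 0.032 | 6.1% |
| 5% / 25% | 2 | 0.5 | 0.034 | 0.159 | 0.126 | 0.063 | 8.9% |
| 5% / 25% | 3 | 0.6 | 0.051 | 0.228 | 0.177 | 0.106 | 16.8% |

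(Gaps use unrounded means.) With B in the model the bias is 0.00 in every row, because those retained at a given B are then comparable across arms.

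**Case 2: dropout also reflects reluctance that B misses.** Let the driver be 0.8 x B + 0.6 x e, where Y = r x B + sqrt(1 - r^2) x e. The factor r in the bias becomes 0.8r + 0.6 sqrt(1 - r^2).

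- 5% / 25%, OR 2, r = 0.5: (0.400 + 0.520) x 0.126 = 0.116 SD. By simulation, about 0.07 SD remains after adjusting for B.
- 5% / 25%, OR 3, r = 0.6: (0.480 + 0.480) x 0.177 = 0.170 SD. About 0.09 SD remains.

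**When the bias vanishes or reverses.** If loss is unrelated to attitude, both means are 0 and so is the bias. If loss is equal and depends on attitude in the same way in each arm, the gap is 0. Equal overall loss is not sufficient by itself: with 15% lost in each arm but only chatbot loss tracking attitude (OR 2, r = 0.5), the bias is 0.5 x 0.098 = 0.049 SD. If favourable parents leave more (OR 0.67), it is about -0.01 to -0.07 SD at 10% to 30% chatbot loss (r = 0.5 to 0.7).

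**Gain without differential dropout.** Adjusting for B multiplies the SE by sqrt(1 - r^2) = sqrt(0.75) = 0.87 at r = 0.5, a reduction of about 13%.

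**The case against.** The strongest reply is that nothing in the documents shows the bias will occur. The survey takes about 10 minutes, no dropout rate is given, and a loss of 25% against 5% is conjecture. The consent form's title announces HPV vaccine messaging, so some averse parents may decline before assignment, in balance across arms. Controls can also leave when the HPV questions appear. With 5% versus 10% loss the bias is about a tenth of the pairwise standard error. All of this stands, and it is why the point is conditional.

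Three stronger readings are tempting and are not supported.

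- A reader might infer that the planned analysis favours the chatbot arms and that type I error exceeds its nominal level. That needs dropout that differs by arm in a way that leaves more favourable parents in the chatbot arms. The documents show no such pattern, and other patterns give zero or opposite bias.
- A reader might infer that the SAP prescribes a completers-only analysis adjusted for demographics alone. It does not. Using only those with outcomes is the default behaviour of an ANCOVA where the SAP is silent, and its covariate sentence gives examples, though all are demographic.
- A reader might infer that paying completers causes the bias. The rule applies to all three arms and encourages finishing, so it creates no imbalance by itself. It matters only because a parent who abandons the chatbot has no stated paid route to the outcome items.

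What survives is the unequal path to the outcome and the absence from the stated model of a relevant variable that is already collected.

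**Conclusion.** The concern holds as a conditional risk. If loss is higher in the chatbot arms and falls mainly on hesitant parents, the chatbot-versus-control contrasts on attitudes and intentions can be biased toward benefit. Under the stated assumptions the bias is about 0.01 to 0.11 SD when dropout follows baseline attitude, and up to about 0.17 SD when unmeasured reluctance contributes. Against d = 0.2, an assumed value for a small effect, that is 5% (0.010 / 0.2) to 53% (0.106 / 0.2), and 85% (0.170 / 0.2) at the extreme. The sizes rest entirely on assumed dropout rates, odds ratios and correlations.

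The personalized versus non-personalized contrast is affected only if loss differs between those two arms, which the documents give no reason to expect.

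The change is worth making because it is cheap, does not depend on the direction of any bias, and improves precision even if dropout proves harmless.

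**What to change.** 1. **SAP, covariates.** Add the childhood-vaccine attitude score, taken before the chatbot, to the ANCOVAs and to the first regression block. This removes the bias when dropout depends on that score, reduces it otherwise (about 0.12 to 0.07 SD in the middle example), and shrinks the standard error by about 13% at r = 0.5. It costs one sentence and no new data.

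2. **Protocol section 3, survey routing.** Send participants who stop the chatbot early to the HPV attitude and intention items, and treat reaching those items as completion for payment. State in the SAP that everyone with outcomes is analysed in the assigned arm, whether or not they engaged with the chatbot. The cost is $1-$2 per extra person paid and slight dilution: with 10% non-engagement, d = 0.20 becomes 0.9 x 0.20 = 0.18. Routing must be settled before data collection, since outcomes never asked for cannot be recovered.

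3. **SAP, reporting.** Report loss after assignment by arm and by baseline attitude. Add one sensitivity analysis for missing outcomes, with its range justified in advance. Multiple imputation from arm, baseline attitude and demographics rests on the same assumption as the adjusted model in item 1 and adds almost nothing, so it would not serve as that sensitivity analysis.
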